## TRADEMARK INFORMATION

Trademarks of the GSK group of companies
NONE

Trademarks not owned by the GSK group of companies
GastroPlus
EnteroTracker
MedDRA
WinNonlin

**10.13. Appendix 13: Protocol Amendment History**

The Protocol Amendment Summary of Changes Table for the current amendment is located directly before the Table of Contents (TOC).

**Amendment 09: 22 July 2024**

**Overall rationale for the Amendment:** Changes were provided in this amendment in response to questions by a regulatory agency.

Section # and Name	Description of Change	Brief Rationale
CCI [REDACTED] [REDACTED] [REDACTED] [REDACTED] [REDACTED]	Adjusted timings of baseline urine assessments, removed duplicate urine drug test	Minimise test burden and ensure appropriate timing of baseline assessments
5.2.2 Exclusion Criteria for PLWCHB	Updated exclusion criterion 24 to specifically mention mental health conditions	Ensure that mental health conditions are explicitly mentioned to ensure due consideration in evaluation of exclusion criteria
5.2.2 Exclusion Criteria for PLWCHB	Specified the year of derivation for the CKD-EPI formula to be used for GFR calculations	Ensure the intended formula is used across sites
6.1 Study Intervention(s) Administered	Additional rows and information added regarding roles of products used within the trial	Clarify all details relating to roles of products used within the trial
6.8 Concomitant Therapy	CCI [REDACTED] [REDACTED] [REDACTED] [REDACTED]	Align protocol provided information with Investigator's Brochure
8.3.7.1 Neuropathy and Neurocognitive events	Added information to indicate that participants experiencing neurocognitive symptoms should be advised to avoid driving and operating heavy machinery.	Align protocol provided information with Investigator's Brochure and Patient Information Sheet/ICF
10.2 Appendix 2: Clinical Laboratory Tests	Specified the CKD-EPI formula to be used for GFR calculations	Ensure the intended formula is used across sites
10.2 Appendix 2: Clinical Laboratory Tests	Clarified that urinalysis may be performed using automated systems	Ensure methods of urinalysis are accurately described

**Amendment 08:** 26 March 2024

CCI

CCI

CCI

CCI

CCI

CCI

CCI

CCI

CCI

CCI

CCI

CCI

CCI

CCI

**Amendment 07**, 29 January 2024

CCI

**Amendment 06, 01 December 2023**

CCI

CCI

CCI

CCI

CCI

CCI

CCI

CCI

CCI

CCI

CCI

CCI

CCI

CCI

CCI

CCI

CCI

CCI

**Amendment 05, 09 March 2023**

CCI

CCI

CCI

CCI

CCI

CCI

CCI

CCI

CCI

CCI

CCI

**Amendment 04**, 06 December 2022

CCI

CCI

**Amendment 03, 26 August 2022**

CCI

CCI

**Amendment 02: 25 April 2022**

CCI

CCI

**Amendment 01: 31 March 2022**

CCI

Table 17	Study Period Definition.....	39
Table 18	Definitions of Assessment Windows for Early discontinuation	40

LIST OF FIGURES

	PAGE
Figure 1	
Participants receiving GSK3965193 or Placebo monotherapy only.	14
Figure 2	
Participants with HBsAg levels ≤ 3000 IU/mL at screen who choose to receive optional open label bepirovirsen treatment.	14

VERSION HISTORY

SAP Version	Approval Date	Protocol Version (Date) on which SAP is Based	Change	Rationale
SAP	30 May 2024	Protocol Amendment Version 8.0 (26 March 2024)	Original Version	Statistical Analysis Plan for Part 3
SAP Amendment 1	26 May 2025	Protocol Amendment Version 10.0 (10 March 2025)	Section 1.: Details on Intercurrent event have been updated	Clarification
			Section 3: Additional text has been added for Randomized, PK and PD analysis set in defining the population and how the data will be reported	Clarification
			Section 4. Added the imputation value to be used for the biomarkers value if they turn out to be LLOQ or TND. Methodology has been added for the derivation of log10 Change from Baseline for HBsAg and Maximum reduction of log10 HBsAg	Clarification

SAP Version	Approval Date	Protocol Version (Date) on which SAP is Based	Change	Rationale
			Removed CCI [REDACTED] CCI [REDACTED] CCI [REDACTED] from Parameters list in the Table 4 as they are in the collect and hold strategy list Methodology to summarize laboratory, vital signs and ECG Data has been updated Additional summaries related to TEAEs are added	
			Section 6. Updated the information on PCI criteria and Assessment window	Clarification
SAP Amendment 2	01 August 2025	Protocol Amendment Version 10.0 (10 March 2025)	4.4.2.4 Additional details on the analysis to understand target engagement added	Detailed specification
SAP Amendment 3	07 Apr 2026	Protocol Amendment Version 10.0 (10 March 2025)	Section 4.3.1.2.3: Updated the derivation of TEAEs for Bepi period	Clarification and Detailed specification

SAP Version	Approval Date	Protocol Version (Date) on which SAP is Based	Change	Rationale
			Section 4.4.3: Reduced Number of PK parameters which will be assessed for Bepi period	

1. INTRODUCTION

The purpose of this Statistical Analysis Plan (SAP) is to describe the planned analyses for study Part 3 to be included in the Clinical Study Report for Protocol 214760. All details of the interim analyses will be outlined in a separate Interim Analysis Charter.

Statistical Analysis Plan for parts 1 and 2 are documented in a separate plan document and stored in Veeva Vault (TMF-14543291).

1.1. Objectives, Estimands and Endpoints

Objectives	Endpoints
Part 3 and Part 4 (participants living with chronic hepatitis B infection [PLWCHB])	
Primary	

 To assess the safety and tolerability of oral administration of GSK3965193 monotherapy (Part 3) and in combination with bepirovirsen (Part 4) 	
 Incidence of AEs, SAEs, withdrawals due to AEs Incidence of clinically significant laboratory parameters (haematology, clinical chemistry, urinalysis), vital signs, cardiac parameters (electrocardiogram), and sensory nerve conduction

 To evaluate pharmacodynamic (PD) effect of GSK3965193 monotherapy in PLWCHB (Part 3) 	
 Maximum reduction of serum HBsAg levels from baseline CCI [REDACTED] CCI [REDACTED] CCI [REDACTED]
Secondary	

 To evaluate the PK characteristics of repeat doses of GSK3965193 in PLWCHB (Part 3) 	
 AUC(0-tau), Cmax, Tmax, and apparent terminal half-life (T1/2) will be calculated as data permits

 To evaluate pharmacodynamic (PD) effect of GSK3965193 monotherapy in PLWCHB (Part 3) 	
 ≥0.5x log IU/mL reduction of serum HBsAg levels from baseline anytime during the study (on-treatment and post-treatment)

 To assess the safety and tolerability of bepirovirsen monotherapy in PLWCHB who have completed GSK3965193/placebo monotherapy (Part 3) 	
 Incidence of AEs, SAEs, withdrawals due to AEs Incidence of clinically significant laboratory parameters (haematology, clinical chemistry, urinalysis), vital signs
Exploratory	

CCI

Objectives	Endpoints
CCI	

1.1.1. Primary Estimand

The primary clinical question of interest is: What is the difference in maximum reduction of HBsAg from baseline CCI in GSK3965193 vs. placebo in participants living with chronic hepatitis B infection, prior to prohibited medication use or temporary/permanent discontinuation of treatment?

Attributes of Estimand:

Variable/Endpoint	Treatment	Population	Population Summary
Maximum reduction of serum HBsAg levels from baseline CCI CCI CCI CCI	GSK3965193 and Placebo	PLWCHB treated on stable nucleos(t)ide analog (NA) therapy	Mean of maximum reduction in change from baseline over all patients in GSK3965193 and Placebo. Treatment difference (GSK3965193 – Placebo).

Intercurrent Event			Strategy	
Intercurrent Event	Details on the Intercurrent Event	Decision on the usage of data	Strategy	Rationale
Temporary or permanent discontinuation of dosing	Temporary or permanent discontinuation of IP dose include any of the following occurrences: 
 Missing 2 or more consecutive doses Permanent discontinuation from treatment Permanent discontinuation from study 	Data from Day 1 (post randomization) until start of temporary discontinuation or permanent discontinuation.	While on-treatment	Data will only be used until the start of temporary discontinuation or date of permanent discontinuation. This is to capture that the participant could not tolerate the study treatment as planned.

CCI

CCI

1.1.2. Secondary Estimand

The primary clinical question of interest is: What is the difference in the proportion of responders (reduction of serum HBsAg levels ≥ 0.5 log IU/mL) from baseline CCI CCI) of GSK3965193 vs. placebo in participants living with chronic hepatitis B prior to prohibited medication use or temporary/permanent discontinuation of treatment?

Attributes of Estimand:

Variable/Endpoint	Treatment	Population	Population Summary
≥ 0.5 log IU/mL reduction in serum HBsAg levels from baseline CCI CCI CCI CCI	GSK3965193 and Placebo	PLWCHB treated on stable NA therapy	Proportion of responders

Intercurrent events will be handled in the same way as the primary endpoint (see Section 1.1.1).

1.1.3. Supplementary Estimand

The supplementary estimand will only be explored if >20% (4 or more) participants experience any intercurrent event.

The primary clinical question of interest is: What is the difference in maximum reduction of HBsAg from baseline CCI CCI) of GSK3965193 treatment vs. placebo on participants living with chronic hepatitis B infection regardless of usage of prohibited medication or temporary/permanent discontinuation?

Attributes of Estimand:

Variable/Endpoint	Treatment	Population	Population Summary
Maximum reduction of serum HBsAg levels from baseline CCI CCI CCI CCI	GSK3965193 and Placebo	PLWCHB treated on stable NA therapy	Mean of maximum reduction in change from baseline over all patients in GSK3965193 and Placebo. Treatment difference (GSK3965193 – Placebo).

Intercurrent Event			Strategy	
Intercurrent Event	Details on the Intercurrent event	Decision on the usage of data	Strategy	Rationale
Temporary or permanent discontinuation of dosing	Temporary or permanent discontinuation of dose may include any of the following occurrences: 
 • Missing 2 or more consecutive doses • Permanent discontinuation from treatment • Permanent discontinuation from study 	Any data available will be used	Treatment policy strategy	Observed data will be used as is to estimate the treatment effect in the scenario where the temporary or permanent discontinuation of dosing had not occurred.

1.2. Study Design

CCI

CCI

2. STATISTICAL HYPOTHESES

There are no formal hypothesis that will be statistically tested in this study.

2.1. Multiplicity Adjustment

Not applicable as no formal statistical hypothesis will be tested.

3. ANALYSIS SETS

Analysis Set	Definition / Criteria	Analyses Evaluated
Screened	All participants who were screened for eligibility.	Study Population
Enrolled	All participants who passed the screening and entered the study (who were randomized and/or received or not received study intervention or underwent a post-screening procedure). NOTE: screening failures (who never passed screening even if rescreened) and participants screened but never enrolled into the study (Met eligibility but not needed) are excluded from the Enrolled Analysis set as they did not enter the study.	Study Population

Analysis Set	Definition / Criteria	Analyses Evaluated
Randomized	
All participants who were randomly assigned to study intervention.
 
NOTE: The screened, enrolled and randomized sets must be nested, i.e. the enrolled set must be a subset of the screened set, the randomized set must be a subset of the enrolled set.
 
Data will be reported according to randomized treatment.
	Study Population
Safety	
All participants in randomized set who received at least one dose of study intervention.
 
Participants will be assigned to the actual study intervention group if they received that intervention for more than 50% of the cumulative dose.
	Safety
Pharmacokinetic (PK)	
All participants in the Safety analysis set who had at least one non-missing PK assessment, with non-quantifiable (NQ) values considered as non-missing. Furthermore, participants must not have a history of taking prohibited therapies (as per the exclusion criteria), nor have participated in previous clinical studies that are prohibited in the protocol exclusion criteria that might affect the PK exposure assessment.
 
Data will be reported according to the actual study intervention.
	PK
Pharmacodynamic (PD)	
All participants in the Safety analysis set who had at least one non-missing PD assessment and have neither taken any prohibited medication nor participated in previous clinical studies that are prohibited, as defined in the protocol exclusion criteria, which might affect the efficacy assessment.
 
NOTE: Data will be summarized based on randomized treatment.
	PD
Bepirovirsen Extension (OBE)	
All participants who are eligible and opted for Bepirovirsen extension and had received at least one dose of Bepirovirsen will be considered.
	Safety, PK and PD Bepirovirsen

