### 9.3. Analysis Sets

For the purposes of analysis, the following analysis sets are defined:

Population	Description
Enrolled	All participants who passed screening and entered the study.
Intent-to-Treat (ITT)	All participants who received at least 1 dose of study treatment. This population will be based on the treatment the participant was randomized to.
Safety	All participants who received at least 1 dose of study treatment. This population will be based on the treatment the participant received.
Pharmacokinetic (PK) Concentration	All participants in the Safety population who received an active study treatment and had at least 1 non-missing PK assessment (Non-quantifiable [NQ] values will be considered as non-missing values). This population will be used for PK concentration listing.
Pharmacokinetic Parameter	All participants who undergo plasma PK sampling and have evaluable PK parameters estimated. This population will be used for PK parameter listing, plotting of the concentration-time data and PK parameter summary.
Pharmacodynamic (PD)	All participants in the Safety population for whom a Pharmacodynamic sample was obtained and analysed.

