	
 
has substantial periods of contact with a participant and is engaged in their daily health care (e.g., a relative of the participant, a nurse who helps with daily activities in case of residence in a nursing home).
 
 
In the context of a clinical study, a caregiver could include an individual appointed to oversee and support the participant's compliance with protocol-specified procedures.

Certified copy	A copy (irrespective of the type of media used) of the original record that has been verified (e.g., by a dated signature or by generation through a validated process) to have the same information, including data that describe the context, content, and structure, as the original.
Combination product	
Combination product comprises any combination of:
 
 
drug
 
device
 
biological product.
 
 
Each drug, device and biological product included in a combination product is a constituent part.

Comparator	Any product used as a reference (including placebo, marketed product, GSK, or non-GSK) for an investigational product being tested in a clinical trial. This is any product that is being used to assess the safety, efficacy, or other measurable value against the test product (IMP).
Eligible	Qualified for enrollment into the study based upon strict adherence to inclusion/exclusion criteria.
HHS	Deployment of mobile health care professional(s) (nurses or phlebotomists) to perform study activities remotely.
IMP	A pharmaceutical form of an active substance or placebo being tested or used as a reference in a clinical trial, including products already with a marketing authorization but used or assembled (formulated or packaged) in a way different from the authorized form, or when used for an unauthorized indication, or when used to gain further information about the authorized form.
Intercurrent event	Event occurring after study intervention initiation that affects either the interpretation or the existence of the measurements associated with the clinical question of interest.

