4.3.1.2. Main analytical approach

All secondary PK analyses will be based on the PK Analysis Set. PK analysis will be the responsibility of Clinical Pharmacology Modelling and Simulation (CPMS), GSK. Statistical analysis of the derived PK parameter data will be the responsibility of Clinical Statistics, GSK.

Plasma GSK3965193 concentration-time data will be analyzed by non-compartmental methods. Calculations for the final analysis will be based on the actual sampling time points recorded during the study. The various analyses will be conducted as permitted by data available.

For the calculation of the area under the concentration-time curve (AUC), the linear trapezoidal method will be employed for all incremental trapezoids arising from increasing concentrations and the logarithmic trapezoidal method will be used for those arising from decreasing concentrations (i.e., Linear Up/Log Down calculation method). A

minimum number of three data points (not including Cmax) should be used in calculating λ_z .

Unless otherwise specified, all PK analysis for GSK3965193 will be reported using PK set. PD analysis for GSK3965193 will be reported using PD set.

Safety, PK and PD of Bepirovirsen will be reported using the OBE set. These outputs will only be produced if more than 5 participants choose to take part in the optional Bepirovirsen extension arm.

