4.5. Other Safety Analyses

The safety analyses will be based on the Safety Set for GSK3965193, and OBE set for Optional Bepirovirsen arm, unless otherwise specified.

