4.8. Changes to Protocol Defined Analyses

Changes from the originally planned statistical analysis specified in the protocol are detailed in [Table 12](#).

Table 12 Changes to Protocol Defined Analysis Plan

Protocol Defined Analysis	SAP Defined Analysis	Rationale for Changes

 Endpoints for Bepirovirsen optional arm 	
 Cardiac and ECG assessments have not been documented in SAP for Bepirovirsen Optional arm 	
 Cardiac assessment for Bepirovirsen arm has been removed as a secondary objective since cardiac assessment endpoint was incorrectly included in the protocol, and the data is not being collected on the database.

 Definition of Analysis Sets 	
 Definition of PD Analysis Set has been updated to remove any participant who takes a prohibited medication (as per the protocol) pre-treatment. 	
 CCI [REDACTED] CCI [REDACTED] CCI [REDACTED] CCI [REDACTED] CCI [REDACTED] CCI [REDACTED] CCI [REDACTED] There was a need to define an additional analysis population to

Protocol Defined Analysis	SAP Defined Analysis	Rationale for Changes
	
 An additional analysis set, Bepirovirsen Extension (OBE) set has been defined 	
evaluate participants who choose to take part in the optional Bepirovirsen arm

 Estimand 	
 Primary estimand and secondary estimand has been re-defined (clinical question, estimand policy strategy, and estimation of estimand) in Section 1.1.1 and Section 1.1.2 . Also, Supplementary estimand added in Section 1.1.3 as per the suggestion of Estimand SME group. 	
 Following clinical discussion, the estimand framework was updated to align with best practice.

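### The Part 3 SAP makes eligibility a condition of the bepirovirsen analysis set, so a participant injected without meeting the extension's entry condition could be missing from the bepirovirsen safety tables

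*SAP*

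**What the plan says.** Section 3 of the Part 3 SAP defines the OBE set as: "All participants who are eligible and opted for Bepirovirsen extension and had received at least one dose of Bepirovirsen will be considered". Three conditions are joined: eligible, opted in, dosed.

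That set carries the bepirovirsen results. SAP 4.3.1.2 states: "Safety, PK and PD of Bepirovirsen will be reported using the OBE set". SAP 4.5, which covers extent of exposure, states: "The safety analyses will be based on the Safety Set for GSK3965193, and OBE set for Optional Bepirovirsen arm, unless otherwise specified". SAP 6.1 uses the same set for the extension's study population displays.

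The protocol is different. Its Safety population in 9.3 is: "All participants who received at least 1 dose of study treatment. This population will be based on the treatment the participant received". Section 9.4.5 places every safety analysis on that population. The SAP's own Safety set, in the same table as the OBE set, also has no eligibility condition: "All participants in randomized set who received at least one dose of study intervention".

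SAP 4.8, Table 12, records the OBE set as a change from the protocol. The reason given is a need to "evaluate participants who choose to take part in the optional Bepirovirsen arm". Eligibility is not mentioned.

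**The concern.** Safety and tolerability of bepirovirsen is a secondary objective of Part 3. A safety set is normally defined by exposure alone, because a person who received the drug can be harmed by it whether or not they should have received it. Here a programmer who follows the definition as written would drop a dosed participant found not to have met the entry condition. That participant's adverse events, serious events, death, events of special interest, laboratory changes and exposure would then be absent from the bepirovirsen summary tables.

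A breach is possible. Part 3 requires screening HBsAg above 100 IU/mL (Protocol 5.1.3), while the title of SAP Figure 2 limits the extension to 3000 IU/mL or less. Participants who do and do not qualify for the extension can therefore be in the same cohort. Protocol 7.1 adds a second gate: those who stopped monotherapy early need prior Medical Monitor agreement to progress.

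**Working it through.** **Step 1. Compare the sets.**

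| Set | Conditions | Used for |
|---|---|---|
| Protocol 9.3 Safety | dosed | all safety analyses (9.4.5) |
| SAP 3 Safety | randomised, dosed | GSK3965193/placebo safety |
| SAP 3 OBE | eligible, opted in, dosed | bepirovirsen safety, PK, PD, exposure, population displays |

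The extension is optional, so opting in removes essentially nobody who was dosed under the protocol. The operative difference is eligibility.

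**Step 2. Look for another table that recovers the person.** Under SAP 4.2.2.1 the GSK3965193/placebo treatment-emergent window closes 7 days after the last dose. Bepirovirsen starts after a 2-week washout (Protocol 4.2.3). Since 14 days > 7 days, events in the bepirovirsen period fall outside the monotherapy treatment-emergent tables. The only display titled as a deaths summary is in the bepirovirsen list (SAP Table 10), not in Table 5. SAP 4.5 allows exceptions ("OBE set for Optional Bepirovirsen arm, unless otherwise specified"), but none for bepirovirsen safety appears in the visible text.

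**Step 3. Size, by illustration.** The plan gives no figure to reproduce, and the extension size is redacted. Two points bound a plausible range:

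- SAP 4.3.1.2 produces the outputs only if more than 5 participants join, so n = 6 is the smallest case.
- SAP 1.1.3 equates more than 20% of participants with 4 or more. If 4 is the smallest count above 20% of N, then 3 ≤ 0.20N < 4, so N is 15 to 19. I take 19 as the largest case, as an inference and not a stated sample size.

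Assume one dosed participant is ineligible and has the only serious event. The limits are exact (Clopper-Pearson) 95% upper limits. For 0/m the limit is 1 − 0.025^(1/m); for example, 1 − 0.025^(1/5) = 0.522. For 1/n it is the 97.5th percentile of Beta(2, n − 1).

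| Dosed n | Share removed (1/n) | Everyone dosed | OBE read literally |
|---|---|---|---|
| 6 | 16.7% | 1/6 = 16.7%, upper 64.1% | 0/5, upper 52.2% |
| 8 | 12.5% | 1/8 = 12.5%, upper 52.7% | 0/7, upper 41.0% |
| 10 | 10.0% | 1/10 = 10.0%, upper 44.5% | 0/9, upper 33.6% |
| 19 | 5.3% | 1/19 = 5.3%, upper 26.0% | 0/18, upper 18.5% |

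The shift can go the other way. If the one excluded person of 8 has no event and another has the only one, the rate moves from 1/8 = 12.5% to 1/7 = 14.3%.

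**The case against.** The strongest reply is that *eligible* only restates the route into the extension: the option is offered to those under the HBsAg limit, some accept, and they are dosed. Table 12 describes the set as those who choose to take part, which suggests that no filter was intended. Where this SAP means to remove people for prohibited therapies or prior studies under the exclusion criteria, it says so, as in its PK and PD sets. This may well be the intent. It does not settle the matter, because the sentence still makes eligibility a condition and the outputs will be programmed from the sentence.

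A reader might also infer from the protocol glossary, which defines the term as "Qualified for enrollment into the study based upon strict adherence to inclusion/exclusion criteria", that a breach of any Part 3 criterion removes a participant. The documents do not establish that. The glossary concerns enrolment into the study, whereas the OBE sentence concerns the extension, and the HBsAg ceiling is not among the listed inclusion or exclusion criteria.

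It also stands that the data would not vanish. SAP 4.3.1.2.3 lists non-treatment-emergent events, SAP 4.1 keeps participant-level data viewable, and Protocol 9.4.5 calls for review of individual data. Protocol 10.1.5.1 sends bepirovirsen safety data to the IDMC with no eligibility qualifier. Waivers of entry criteria are prohibited (Protocol 5), which makes breaches less likely but does not rule out errors found later.

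**Conclusion.** The concern holds in a limited form. As written, the OBE definition would leave a participant who was injected without meeting the extension's entry condition out of the bepirovirsen summary tables. That departs from Protocol 9.3 and 9.4.5 and from the SAP's own Safety set, and Table 12 does not disclose it. For breaches of general Part 3 criteria, the result depends on how an undefined word is read.

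The size is conditional: nil if no such participant is dosed, otherwise about 5% to 17% of the dosed group per person over the assumed range of 19 down to 6.

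Two stronger readings should be resisted. One is that the exclusion can only hide harm. It can move a rate in either direction; what is certain is that any harm in the excluded person leaves the summaries. The other is that those excluded are the participants at greatest risk. No visible text presents the HBsAg limit as a safety criterion, and Protocol 2.3.2 mentions it in the benefit assessment.

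**What to change.** In SAP Section 3, define the set used for bepirovirsen safety, exposure and disposition by receipt alone, for example: *every participant given one or more doses of bepirovirsen in Part 3, whether or not the entry conditions for the extension were met*. If an eligibility restriction is wanted for the bepirovirsen PK or PD summaries, state it there and say which criteria it refers to. Report breaches through the important-deviation summary already planned in SAP 6.1.3, and record the change in Table 12.

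The cost is a sentence or two of SAP text and the matching population flag. No new data or participants are needed. The only consequence is that anyone dosed in breach of the entry condition appears in the safety tables, as the protocol already requires.
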